**Specific Definitions of Adverse Events:****DEATH**

All deaths are considered cardiac unless a non-cardiac cause can be documented.

- Cardiac death: Any death due to immediate cardiac cause (e.g. MI, low-output failure, fatal arrhythmia). Unwitnessed death and death of unknown cause will be classified as cardiac death.
- Non-cardiac death: Any death not covered by the above definition, including death due to pulmonary causes, accident, suicide, infection, sepsis, or trauma.

**STENT THROMBOSIS**

We intend to use the ARC Definite/Probable definition of stent thrombosis

**Definite Stent Thrombosis:**

- Angiographic or pathologic confirmation of intracoronary stent thrombosis either inside or 5mm proximal or distal to the stent.

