## 1.2 STUDY DESIGN

## 1.3 SCHEDULE OF ACTIVITIES (SOA)

Procedures	Screening/ Baseline a	Index Procedure (Day 1)	Post-Index Procedure b (Prior to discharge)	30 Days (+ 7 days) Post PCI ) (in office)	60 days (+7 days) Post PCI (In office or via phone)	7 months (+14 days i ) Post PCI (In office or via phone)	13 Months (+ 30 days j ) Post PCI (In office or via phone)
Informed Consent	X						
H&P c	X						
CBC w Diff, platelets	X		X				
BMP	X		X				
PT/INR (only if on warfarin, liver disease or severe anemia)	X		X				
CPK, CK-MB or Troponin-I	X		X d				
EKG	X		X				
ConMeds (Only Cardiac)	X		X	X	X	X	X
Cardiac Cath w PCI		X					
ASA LD	X e						
ASA MD		X f		X		X	X
P2Y12 LD		X g					
P2Y12 MD			X h	X		X	X
AE assessment		X	X	X	X	X	X
Angina assessment k				X	X	X	X
Angina Questionnaire				X			
EDC Completion	X	X	X	X	X	X	X

- a to be completed  $\leq$  7 days prior to Index procedure
- b To be completed within 24 hours after Index procedure
- c Determination of high risk of bleeding (HRB)
- d Perform 2, 6-8 hours apart, if cardiac enzyme levels are elevated (i.e. exceed the upper limits of normal as defined by local guidelines), serial measurements be performed until a decline is noted. If same day discharge draw one set immediately post PCI then 2nd set @ 6-8 hours after
- e Aspirin loading dose (LD) = 325 mg. Start day of procedure (if not on chronic ASA)
- f Aspirin maintenance dose (MD) = 81 mg. Start the day after aspirin loading dose
- g P2Y12 Inhibitor Loading Dose (investigator preference): clopidogrel 600 mg PO x 1 or 75 mg PO daily x 4; prasugrel 60 mg PO x 1; ticagrelor 180 mg PO x 1. Start within 7 days of procedure.
- h P2Y12 Inhibitor Maintenance Dose (investigator preference): clopidogrel 75 mg PO daily; prasugrel 10 mg PO daily; ticagrelor 90 mg PO BID. Start day after P2Y12 inhibitor loading dose
- i 6 months post DAPT cessation
- j 12 months post DAPT cessation
- k Angina Assessment only at 60 days, 7 months and 13 months

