**AND**

- Symptoms suggestive of an acute coronary syndrome:
  - New onset of ischemic symptoms at rest (typical chest pain with duration >20 minutes)
  - New ischemic ECG changes suggestive of acute ischemia
  - Typical rise and fall in cardiac biomarkers ( $>2\times$  ULN of CK)

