**Probable Stent Thrombosis:**

- unexplained death within 30 days
- target vessel myocardial infarction without angiographic confirmation of stent thrombosis

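### As Section 8.1.1 is written, an autopsy-proven stent thrombosis that causes death after day 30 with no recorded symptoms, ECG change or biomarker rise is neither definite nor probable

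*Combined protocol and SAP*

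**What the plan says.** Section 8.1.1 opens its stent thrombosis definition with a statement of intent: "We intend to use the ARC Definite/Probable definition of stent thrombosis". It then writes out its own criteria.

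- **Definite.** The first element is "Angiographic or pathologic confirmation of intracoronary stent thrombosis either inside or 5mm proximal or distal to the stent". A separate, bold AND links it to "Symptoms suggestive of an acute coronary syndrome". Three items follow: ischemic symptoms at rest, "New ischemic ECG changes suggestive of acute ischemia", and "Typical rise and fall in cardiac biomarkers", the last with a threshold given in CK only. The text does not say whether one item is enough or all are needed.
- **Probable.** Two routes are listed: "unexplained death within 30 days", and an infarction in the target vessel without angiographic proof of stent thrombosis. The second has no time limit.
- **Spontaneous MI** (same section). A rise and/or fall in a cardiac biomarker, preferably troponin, is mandatory, together with at least one supporting finding. Thrombus seen at autopsy is one of the supporting findings.
- **Death** (same section). A death is cardiac unless a non-cardiac cause is documented, and unwitnessed deaths are explicitly included.

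Sections 1.1 and 3 make ARC definite/probable stent thrombosis a secondary endpoint covering 1 to 13 months after the procedure.

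**The concern.** Because the AND applies to both kinds of confirmation, finding the thrombus in the stent at autopsy does not by itself make the event definite. A patient who dies suddenly or unobserved may leave no symptom history, no ECG and no blood sample. The protocol expects such deaths, since it has a rule for classifying them.

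The probable category does not pick these cases up in the analyzed period. The endpoint starts at 1 month, so a route limited to the first 30 days is essentially inoperative within it.

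Stent thrombosis is named in the narrative hypothesis (Sections 1.1 and 4.1) and among the risks of stopping the P2Y12 inhibitor (Section 2.3.2, under the risks of study participation). A rule that omits a proven case understates the harm the study is meant to characterize, and the error cannot run the other way.

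**Working it through.** The plan gives no figure for this point, so there is none to reproduce. The check applies the Section 8.1.1 criteria to three types of autopsy-proven fatal stent thrombosis after day 30.

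**Case A: no ischemic symptoms, ECG change or biomarker result recorded.**
1. Definite: the pathologic element is met, the acute coronary element is not. The AND fails.
2. Probable, death route: the death is later than 30 days, and after the autopsy it is no longer unexplained. Fails.
3. Probable, MI route: spontaneous MI needs a biomarker rise and/or fall, and autopsy thrombus counts only in addition to it. The procedural MI criteria also rest on CK-MB or troponin. Fails.

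Result: neither definite nor probable.

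**Case B: rest pain, ischemic ECG change or a qualifying biomarker rise and fall recorded before death.** Definite, provided that one of the three items is enough. The text leaves that open.

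**Case C: biomarker rise and/or fall with a value above the 99th percentile, thrombus at autopsy, target vessel, no angiogram.** The spontaneous MI definition is met, so the event is at least probable through the MI route, at any time.

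The gap is therefore Case A only.

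**Weight of one Case A event.** Inputs: N=231 (planned total) and N=100 (initial phase), both from Section 9.2.
- 1 / 231 = 0.0043, or 0.43 percentage points.
- 1 / 100 = 0.010, or 1.0 percentage point.

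**All stent thromboses, for scale.** Section 9.2 quotes historic 1-year rates of 0.3% to 5.3%.
- N=231: 0.003 × 231 = 0.7; 0.053 × 231 = 12.2.
- N=100: 0.003 × 100 = 0.3; 0.053 × 100 = 5.3.

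These are expected totals of stent thrombosis of every kind. They are not estimates of Case A events. They show only that, at the low end of the range, one unclassified case would be as large as the whole expected count.

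**Biomarker item.** Within Section 8.1.1, the stent thrombosis item sets its threshold in CK, while the spontaneous MI definition prefers troponin. The same laboratory result can thus satisfy one definition and have no stated threshold in the other.

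**The case against.** Much of the opposing case stands and limits the point.

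- **The death is still counted.** It enters the primary endpoint as cardiac death, and also all-cause death. Only its label within one secondary endpoint is at risk. Stent thrombosis is not in the formal hypotheses of Section 9.1, nor among the outcomes Section 9.4.2 names for testing.
- **The frequency is unknown.** The documents give no autopsy rate and no fraction of stent thromboses that are suddenly fatal. The number of Case A events could be zero.
- **ARC intent and independent adjudication.** The protocol intends to use ARC, and Section 10.3 makes the independent monitoring committee the events committee. This helps only in part. The written criteria follow the statement of intent, and nothing says which governs if they differ. How far they differ from ARC cannot be judged from these documents.

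Three stronger readings are tempting, and the documents do not support them.

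1. *Every fatal autopsy-proven case after day 30 is lost.* Cases B and C show otherwise.
2. *All three acute coronary items are required, so angiographically proven cases are lost too.* The missing connector is an ambiguity, not a rule. The probable list has the same format, and its two entries are plainly alternatives; where the section wants both elements, it prints AND.
3. *Sites may measure troponin alone, so the CK item cannot be met.* The Section 1.3 row "CPK, CK-MB or Troponin-I" is marked only at screening and before discharge. It says nothing about what is measured when a patient presents between months 1 and 13. The mismatch that does stand is with the MI definition in the same section.

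**Conclusion.** The point holds in a narrow form. An autopsy-proven stent thrombosis causing death after day 30, with no documented ischemic symptoms, ECG change or biomarker rise, is classified as neither definite nor probable. The resulting error in the 1 to 13 month stent thrombosis rate can only be downward. Each such case is worth 0.43 percentage points at N=231 or 1.0 at N=100; the number of cases cannot be estimated from the documents. The primary endpoint is unaffected.

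This rests on two assumptions: that adjudicators apply the criteria as printed, and that autopsy is performed in at least some late sudden deaths. The missing connector and the CK-only threshold are lesser clarity defects in the same definition. The change should be made because it is specific and cheap, although the expected effect on the results is small.

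**What to change.** In Section 8.1.1 and on the adjudication form, define definite stent thrombosis as either:

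- (a) pathologic confirmation, alone; or
- (b) angiographic confirmation AND at least one of: ischemic symptoms at rest, new ischemic ECG changes, or a typical rise and fall in cardiac biomarkers.

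Align the biomarker item with the spontaneous MI definition, so that troponin is accepted as well as CK and its threshold is stated. Say that these written criteria govern adjudication, or, if the ARC text is meant to govern, reconcile the two before the events committee classifies any case.

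The cost is a wording amendment and a revised form. No test or visit is added and patient management does not change. The reported stent thrombosis rate may be slightly higher. If cases have already been adjudicated, those with autopsy findings should be re-read under the revised wording.

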**AND**

- Symptoms suggestive of an acute coronary syndrome:
  - New onset of ischemic symptoms at rest (typical chest pain with duration >20 minutes)
  - New ischemic ECG changes suggestive of acute ischemia
  - Typical rise and fall in cardiac biomarkers ( $>2\times$  ULN of CK)

**Probable Stent Thrombosis:**

- unexplained death within 30 days
- target vessel myocardial infarction without angiographic confirmation of stent thrombosis

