**Secondary Endpoints**

- Rate of cardiac death or myocardial infarction (SCAI definition) from 1 to 13 months post-index procedure in the overall enrolled “intent-to-treat” patient population
- Rate of Academic Research Consortium (ARC) definite/probable stent thrombosis (ST) involving SYNERGY™Stents from 1 to 13 months post-index procedure
- Rate of major bleeding (GUSTO severe/life threatening + moderate) from 1 to 13 months post-index procedure
- Ischemia-Driven (ID) Target Lesion Revascularization,
- ID Target Vessel Revascularization,
- Target Lesion Failure,
- Target Vessel Failure,
- All-Cause Death, and
- All-Cause Death or MI.

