### **3 OBJECTIVES AND ENDPOINTS**

OBJECTIVES	ENDPOINTS	JUSTIFICATION FOR ENDPOINTS
To determine the safety of 1-month DAPT in a HBR patient population who are undergoing SYNERGY stent implantation.	Primary Endpoint: 
 
• Rate of cardiac death or myocardial infarction (SCAI definition) from 1 to 13 months post-index procedure in the “as
 
	The specific endpoints are in accordance with EVOLVE Short DAPT (an approved FDA Trial). The 13 month endpoint

OBJECTIVES	ENDPOINTS	JUSTIFICATION FOR ENDPOINTS
	
treated” (eligible for 30 day DAPT cessation) population.
 
Secondary Endpoints
 
 
• Rate of cardiac death or myocardial infarction (SCAI definition) from 1 to 13 months post-index procedure in the overall enrolled “intent-to-treat” patient population
 
• Rate of Academic Research Consortium (ARC) definite/probable stent thrombosis (ST) involving the SYNERGY Stent’s at 1 to 13 months post-index procedure
 
• Rate of major bleeding (GUSTO severe/life threatening + moderate) at 1 to 13months post-index procedure
 
• Ischemia-Driven (ID) Target Lesion Revascularization,
 
• ID Target Vessel Revascularization,
 
• Target Lesion Failure,
 
• Target Vessel Failure,
 
• All-Cause Death, and
 
• All-Cause Death or MI.
 
	is also in accordance with EVOLVE Short DAPT, in that the primary outcome is measured 12 months following DAPT cessation.

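### The probable stent-thrombosis rule is over-inclusive: a target-vessel MI counts even when angiography shows an open SYNERGY stent and another culprit

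*Combined protocol and SAP*

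**What the plan says.** The synopsis (1.1) lists as a secondary endpoint the rate of "definite/probable stent thrombosis (ST) involving SYNERGY™Stents from 1 to 13 months post-index procedure". The table in section 3 repeats it with the same window. The hypothesis in 1.1 and 4.1 names ST next to cardiac death or MI.

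Section 8.1.1 says "We intend to use the ARC Definite/Probable definition of stent thrombosis" and then prints working criteria:

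- **Definite ST** needs angiographic or pathologic confirmation in or near the stent, together with a second condition, "Symptoms suggestive of an acute coronary syndrome". Three items follow that condition, with no statement of how many are needed.
- **Probable ST** is either "unexplained death within 30 days" or "target vessel myocardial infarction without angiographic confirmation of stent thrombosis".

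The documents do not define target-vessel MI. Section 10.3 makes the data safety monitoring committee the clinical events committee as well, but gives no rule for adjudicating ST.

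**The concern.** The MI route to probable ST is defined by the absence of a finding. It does not separate two different situations: no angiogram was done, so thrombosis could be neither shown nor excluded; or an angiogram was done and showed the stent open. Both lack confirmation. In the second, the evidence against thrombosis is the very thing that lets the case qualify.

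ST is one of the two risks that section 2.3 specifically names for stopping the P2Y12 inhibitor, and this pilot is meant to inform larger trials. Its ST rate should not include MIs that the angiogram attributes to something other than the stent.

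**Working it through.** No arithmetic decides this point. The check is to read the definitions in 8.1.1 against each other.

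**Step 1: can an MI be diagnosed without stent thrombus?** Yes. Spontaneous MI needs a biomarker rise or fall plus at least one of five items. Intracoronary thrombus is only one of the five.

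**Step 2: what does the MI branch require?** (a) an MI, (b) in the target vessel, (c) with ST not confirmed by angiography. It does not require that angiography was not done, that the ischaemia lay in the stented territory, or that no other cause was found.

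**Step 3: apply the rule to four cases in months 1 to 13.**

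| Case | As written | With the wording under fix |
|---|---|---|
| Target-vessel MI, ST confirmed on angiography, acute coronary features present | Definite | Definite |
| MI in the stented territory, no angiogram or autopsy, no other cause evident | Probable | Probable |
| Target-vessel MI, angiogram shows the stent open and a new culprit elsewhere in that vessel | Probable | Not ST |
| MI in a vessel that was not treated | Not ST | Not ST |

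Only the third row differs, and it is the misclassification. The narrower rule selects a subset of the present one, so for this branch the present wording can only add events.

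**Step 4: what can be said about size?** Section 9.2 gives historic one-year ranges of 0.3 to 5.3% for ST and 1.9 to 8.8% for MI. In 231 patients:

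- ST: 231 × 0.003 = 0.7 to 231 × 0.053 = 12.2 events
- MI: 231 × 0.019 = 4.4 to 231 × 0.088 = 20.3 events

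The excess would be the MI count times the share that are target-vessel MIs with an open stent or another cause on angiography. The documents give no figure for that share, so the product cannot be formed. What can be stated is the effect of one such event: 1/231 = 0.43 percentage points, or 1/100 = 1.0 point in the initial phase. This takes all 231 or 100 patients as the denominator; a smaller analysed set makes it larger.

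**Step 5: does it reach the primary endpoint or the sample size?** No. An MI counts in cardiac death or MI whether or not it is also labelled ST. The sample size rests on p0 = 0.031, p1 = 0.0047, one-sided alpha 0.05 and power 0.95. The normal approximation gives

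n = [(1.645 × √(0.031 × 0.969) + 1.645 × √(0.0047 × 0.9953)) / (0.031 − 0.0047)]² ≈ 229,

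close to the stated 231. The wording of the trial's ST definition is not an input.

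**The case against.** The best defence is that the bullet should not be read alone. The endpoint is confined to ST involving SYNERGY stents, and an MI from a new culprit with a visibly open stent is hard to describe that way. Section 8.1.1 names ARC as the standard, so the bullet may be shorthand for a fuller text. A committee will adjudicate, and section 10.1.6 promises a charter that defines the data elements it needs.

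Part of this stands: a sensible adjudicator might well reject the open-stent case. But the SYNERGY phrase says which device counts, not what shows that it thrombosed. ARC is stated as an intention, followed by printed criteria that omit the limiting conditions; the ARC text is not in the documents, so whether it would narrow them cannot be checked. The committee has a role but no written ST rule.

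The defence is also right that the consequence is limited. This is a secondary endpoint in a single-arm pilot, and section 9.4.2 does not name ST among the safety outcomes to be tested.

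A reader might infer more, and the documents do not support it:

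- **That the 30-day death branch is a defect because the endpoint starts at month 1.** ST is collected from sheath insertion to the 13-month visit, so the branch has a function early on. Later unexplained deaths are not lost: "Unwitnessed death and death of unknown cause will be classified as cardiac death". They therefore enter the cardiac death or MI endpoints.
- **That a line for possible ST is missing.** The plan chose definite and probable. A third category is a preference, not a correction.
- **That definite ST needs all three listed items, so proven thromboses would be dropped.** The list has no connector. That is an ambiguity, not a stated requirement.

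**Conclusion.** The point holds for the MI branch of probable ST. As printed, it counts a same-vessel MI with an open SYNERGY stent and another culprit, and no written rule removes it. This rests on reading 8.1.1 literally, which is reasonable because those are the only criteria supplied.

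The size of the excess is not known. A reader might be tempted to assume that half of MIs qualify, take 0.5 × 1.9% = 0.95%, and conclude that ST would rise from 0.3% to 1.25%. That does not follow. The half has no source. It counts every target-vessel MI without proven thrombosis, including those with no angiogram that may properly remain probable ST. Adding it to 0.3% also assumes that the historic ST rate contains no probable cases, which section 9.2 does not say.

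The primary endpoint and N = 231 stand. The correction is still worth making: ST is part of the hypothesis, and at the low end of the historic range (0.7 events expected in 231) a single misclassified MI would matter.

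**What to change.** In 8.1.1, restrict the MI branch of probable ST to an MI in the territory of an implanted SYNERGY stent, where angiography or autopsy has not excluded stent thrombosis and no other cause is evident. State in 10.3 or the committee charter that the committee acting as CEC adjudicates ST to that text.

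As a minor clarification, put a lead-in above the three acute-coronary-syndrome items under definite ST saying that at least one is required, as the spontaneous MI definition already does for its own list.

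The cost is a change of definition wording, with the IRB review that any amendment needs. MI, death and ST events are already collected through the 13-month visit, so no new data or staff are needed.

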**GUSTO Severe/life-threatening or moderate bleeding**

- Severe or life-threatening: Either intracranial hemorrhage or bleeding that causes hemodynamic compromise and requires intervention
- Moderate: Bleeding that requires blood transfusion but does not result in hemodynamic compromise

**MYOCARDIAL INFARCTION –SCAI Definition – Procedural Related MI****Group                      Definition**

**Normal baseline CK-** CK-MB rise of  $\geq 10$  ULN or  $\geq 5$  ULN with new pathologic Q-waves in at least 2 contiguous leads or new persistent left bundle branch block  
**MB**  
OR  
In the absence of baseline CK-MB, a cTn rise of  $\geq 70$  ULN or a rise of  $\geq 35$  ULN plus new pathologic Q-waves in at least 2 contiguous leads or new persistent left bundle branch block

**Elevated baseline** A CK-MB or cTn rise that is equal (by an absolute increment) to the **biomarkers that are** definitions described for patients with normal CK-MB at baseline. **stable or falling**

**Elevated baseline** A CK-MB or cTn rise that is equal (by an absolute increment) to the **biomarkers that** definitions described for patients with normal CK-MB at baseline  
**have not been** *Plus*  
**shown to be stable** New ST-segment elevation or depression  
**or falling** *Plus*  
New-onset or worsening heart failure or sustained hypotension or other signs of a clinically relevant MI.

#### **Spontaneous MI:**

Detection of a rise and/or fall of cardiac biomarker values [preferably cardiac troponin (cTn)] with at least one value above the 99th percentile upper reference limit (URL) and with at least one of the following:

- Symptoms of ischemia
- New or presumed new significant ST-segment-T wave (ST-T) changes or new left bundle branch block (LBBB)
- Development of pathological Q waves in the ECG
- Imaging evidence of new loss of viable myocardium or new regional wall motion abnormality
- Identification of an intracoronary thrombus by angiography or autopsy

---

#### 8.1.2 DEFINITION OF SERIOUS ADVERSE EVENTS (SAE)

An adverse event (AE) or suspected adverse reaction is considered "serious" if, in the view of either the investigator or sponsor, it results in any of the following outcomes:

- death, a life-threatening adverse event,

- inpatient hospitalization or prolongation of existing hospitalization,
- a persistent or significant incapacity or substantial disruption of the ability to conduct normal life functions,

Important medical events that may not result in death, be life-threatening, or require hospitalization may be considered serious when, based upon appropriate medical judgment, they may jeopardize the participant and may require medical or surgical intervention to prevent one of the outcomes listed in this definition.

---

